7.1 ADVERSE EVENTS

An AE means any untoward medical occurrence associated with the use of a drug in humans, whether or not considered drug related. An AE can therefore be any unfavorable and unintended sign (including an abnormal laboratory finding, for example), symptom, or disease temporally associated with the use of investigational product, whether or not considered related to the investigational product.

7.2 LIFE-THREATENING ADVERSE EVENT OR LIFE-THREATENING SUSPECTED ADVERSE REACTION

An AE or suspected adverse reaction is considered "life-threatening" if, in the view of either the investigator or sponsor, its occurrence places the patient or subject at immediate risk of death. It does not include an AE or suspected adverse reaction that, had it occurred in a more severe form, might have caused death.

7.3 SERIOUS ADVERSE EVENT OR SERIOUS SUSPECTED ADVERSE REACTION

A Serious Adverse Event (SAE) or serious suspected adverse reaction is considered “serious” if, in the view of either the investigator or sponsor the event:

- Results in death
- Is life-threatening (defined as an event in which the subject was at risk of death at the time of the event; it does not refer to an event which hypothetically might have caused death if it were more severe)
- Requires inpatient hospitalization or causes prolongation of existing hospitalization (see note below for exceptions)
- Results in persistent or significant disability/incapacity
- Is a congenital anomaly/birth defect
- Is an important medical event, defined as a medical event that may not be immediately life-threatening or result in death or hospitalization but, based on appropriate medical and scientific judgment, may jeopardize the subject or may require intervention (*e.g.*, medical, surgical) to prevent one of the other serious outcomes listed above. Examples of such events include but are not limited to intensive treatment in an emergency department or at home for allergic bronchospasm; blood dyscrasias or convulsions that do not result in hospitalization.

All pregnancies, regardless of outcome, should be reported to the Sponsor, including pregnancies that occur in the female partner of a male study subject. All pregnancies should be followed to outcome.

Although overdose (PEX >1,200 ng/ml) is not always serious by regulatory definition, this event should be reported as an SAE in this study. Suspected overdose associated with lower PEX systemic levels should also be reported as an AE or SAE if warranted by the clinical history and/or laboratory findings. Alternative explanations, such as a change in medications that may alter the patient’s CYP2D6 metabolism, should be considered.

Cancer, also, is not always serious by regulatory definition; this event (excluding basal-cell or squamous-cell carcinomas of the skin) should be reported to the Sponsor at the earliest possible moment.

NOTE: The following hospitalizations are not considered SAEs in the Sponsor’s clinical studies:

- A visit to the emergency room or other hospital department lasting less than 24 hours that does not result in admission (unless considered an “important medical event” or a life threatening event)
- Elective surgery planned before signing consent
- Admissions as per protocol for a planned medical/surgical procedure
- Routine health assessment requiring admission for baseline/trending of health status (*e.g.*, routine colonoscopy)
- Medical/surgical admission for purpose other than remedying ill health state that was planned before study entry. Appropriate documentation is required in these cases.
- Admission encountered for another life circumstance that carries no bearing on health status and requires no medical/surgical intervention (*e.g.*, lack of housing, economic inadequacy, caregiver respite, family circumstances, administrative).

7.4 SUSPECTED ADVERSE REACTION

Suspected adverse reaction means any AE for which there is a reasonable possibility that the drug caused the AE. For the purposes of IND safety reporting, “reasonable possibility” means there is evidence to suggest a causal relationship between the drug and the AE. Suspected adverse reaction implies a lesser degree of certainty about causality than adverse reaction, which means any AE caused by a drug.

7.5 UNEXPECTED ADVERSE EVENT OR UNEXPECTED SUSPECTED ADVERSE REACTION.

An AE or suspected adverse reaction is considered “unexpected” if it is not listed in the investigator brochure or is not listed at the specificity or severity that has been observed; or, if an investigator brochure is not required or available, is not consistent with the risk information described in the general investigational plan or elsewhere in the current application, as amended. For example, under this definition, hepatic necrosis would be unexpected (by virtue of greater severity) if the investigator brochure referred only to elevated hepatic enzymes or hepatitis. Similarly, cerebral thromboembolism and cerebral vasculitis would be unexpected (by virtue of greater specificity) if the investigator brochure listed only cerebral vascular accidents. “Unexpected,” as used in this definition, also refers to AEs or suspected adverse reactions that are mentioned in the investigator brochure as occurring with a class of drugs or as anticipated from the pharmacological properties of the drug, but are not specifically mentioned as occurring with the particular drug under investigation.

7.6 ASSIGNMENT OF ADVERSE EVENT INTENSITY AND RELATIONSHIP TO PERHEXILINE

All AEs, including those that are serious, will be graded by the investigator as follows [NCI Guidelines, 2013]:

- Mild (Grade 1): asymptomatic or mild symptoms; clinical or diagnostic observations only; intervention not indicated.
- Moderate (Grade 2); minimal, local, or non-invasive intervention (e.g., packing, cautery) indicated; limiting age-appropriate instrumental activities of daily living.
- Severe (Grade 3): medically significant but not immediately life-threatening; hospitalization or prolongation of hospitalization indicated; disabling; limiting self-care ADL.

The following categories and definitions of causal relationship to investigational product as determined by a physician should be used [NCI Guidelines, 2013]:

- Unrelated: The AE is clearly not related to the intervention
- Possibly related: The AE may be related to the intervention
- Probably Related: The AE is likely related to the intervention.
- Definitely Related: The AE is clearly related to the intervention.

7.7 COLLECTION AND REPORTING OF ADVERSE EVENTS

AEs can be spontaneously reported or elicited during open-ended questioning, examination, or evaluation of a subject. To prevent reporting bias, subjects should not be questioned regarding the specific occurrence of one or more AEs.

If known, the diagnosis of the underlying illness or disorder should be recorded, rather than its individual symptoms. The following information should be captured for all AEs:

- Onset,

- Duration,
- Intensity,
- Seriousness,
- Relationship to investigational product,
- Action taken,
- Treatment, if required.

If treatment for the event was administered, it should be recorded in the medical record. The investigator must supply the Sponsor and the Institutional Review Board/Independent Ethics Committee (IRB/IEC) with any additional information requested, notably for reported deaths of subjects.

Completion of supplemental case report forms (CRFs) may be requested for AEs and/or laboratory abnormalities that are reported/identified during the course of the study.

7.7.1 Reporting Serious Adverse Events or Serious Suspected Adverse Reaction

Following the subject's written consent to participate in the study, all SAEs must be collected, including those thought to be associated with protocol-specified procedures. Collection of all SAEs should continue for 30 days after the last administration of PEX. If applicable, SAEs must be collected that relate to any later protocol-specified procedure. The investigator should notify the Sponsor of any SAE occurring after this time period that is believed to be related to the investigational product or protocol specified procedure.

If the investigator believes that an SAE is not related to the investigational product but is potentially related to the conditions of the study (such as withdrawal of previous therapy, or a complication of a study procedure), the potential relationship should be specified in the narrative section of the SAE report.

As part of the investigation and reporting of all SAEs, every attempt will be made to obtain a blood sample for analysis of PEX, CIS and TRANS as soon as possible after awareness of the event.

7.7.2 Handling of Expedited Safety Reports

In accordance with local regulations, the Sponsor will notify investigators and appropriate regulatory authorities of all unexpected SAEs having a "reasonable possibility" that the drug caused the event (*i.e.* there is evidence to suggest a causal relationship between the drug and the AE) /serious unexpected suspected adverse reactions (SUSARs).

Other important findings that the Sponsor may report as Expedited Safety Reports (ESR) include increased frequency of a clinically significant expected SAE, an SAE considered associated with study procedures that could modify the conduct of the study, lack of efficacy that poses significant hazard to study subjects, clinically significant safety findings from a nonclinical (*e.g.*, animal) study, important safety recommendations from a study data monitoring committee, or the decision by the Sponsor to end or temporarily halt a clinical study for safety reasons.

Upon receiving an ESR from the Sponsor, the investigator must review and retain the ESR with the Investigator Brochure. Where required by local regulations or when there is a central IRB/IEC for the study, the Sponsor will submit the ESR to the appropriate IRB/IEC. The investigator and IRB/IEC will determine if the informed consent requires revision. The investigator should also comply with the IRB/IEC procedures for reporting any other safety information.

In addition, the Sponsor will report suspected serious adverse reactions (whether expected or unexpected) to the relevant health authorities in all concerned countries according to local regulations (either as expedited and/or in aggregate reports).

7.7.3 Non-serious Adverse Events

Following the subject's written consent to participate in the study, the investigator will begin collecting non-serious AE (NSAE) information. All identified NSAEs must be recorded and described on the AE case report form. If an ongoing NSAE worsens in its intensity, or if its relationship to the investigational product changes, a new NSAE entry for the event should be completed. NSAEs should be followed to resolution or stabilization, or reported as SAEs if they become serious. Follow up is also required for drug-related NSAEs that cause interruption or discontinuation of investigational product, or those that are present at the end of study participation. Subjects with drug-related NSAEs at study completion should receive post-treatment follow up as appropriate.

7.8 LABORATORY TEST ABNORMALITIES

All laboratory test results captured as part of the study should be recorded following institutional procedures. When reporting a test result that constitutes an AE, the clinical term should be used; for example, the event should be reported as "anemia" not "low hemoglobin." Test results that constitute SAEs should be documented and reported as such.

7.9 ADVERSE DEVICE EFFECTS

If an AE or SAE is determined to have been the result of a PEX-CIS assay abnormality (e.g., false positive, false negative, measurement error), it will be deemed an ADE or a Serious ADE (SADE) for the purpose of device reporting and statistical analysis.

7.9.1 Definitions

Adverse device effect (ADE): AE related to the use of an investigational medical device (PEX-CIS assay in the study).

Serious adverse device effect (SADE): ADE that has resulted in any of the consequences characteristic of a serious AE.

7.9.2 Reporting of ADEs

When assessing, recording, and reporting ADEs or SADEs, the same intensity grading system (Section 7.6) and reporting period (Sections 7.7.1 and 7.7.3) will be used for collecting and reporting of AEs.

ADEs will be reported on a separate ADE report form.

7.9.3 Unanticipated Adverse Device Effect (UADE)

An ADE or SADE is considered "unanticipated" if it was not previously identified in nature, severity, or degree of incidence in the investigational plan or application, or any other unanticipated serious problem associated with a device that relates to the rights, safety, or welfare of subjects.

The sponsor will immediately conduct an evaluation of any UADE.

7.10 PEX OVERDOSE

A PEX overdose is defined as the accidental or intentional ingestion or infusion of any dose of a product that results in a systemic level of PEX >1,200 ng/mL. All occurrences of overdose with a systemic PEX level > 1,200 ng/mL must be reported as an SAE. Suspected overdose associated with lower PEX systemic levels should also be reported as an AE or SAE if warranted by the clinical history and/or laboratory findings. Alternative explanations, such as

a change in medications that may alter the patient's CYP2D6 metabolism, should be considered.

7.11 PREGNANCY

Before study enrollment, women of child-bearing potential should be adequately advised on the potential risks versus benefits of PEX by the Investigator, including the potential risks to a human fetus.

7.11.1 Pregnancy Testing

Pregnancy testing will be performed as outlined in Section 6. If the pregnancy of a female study participant is discovered during the treatment period, the study medication should be discontinued.

7.11.2 Reporting of Pregnancy

If, while taking PEX, it is discovered that a study subject is pregnant or may have been pregnant at the time of investigational product exposure, including during at least 6 half-lives after administration, the investigator will notify the Sponsor of this event and record the pregnancy on the Pregnancy Surveillance Form (not on an SAE form). Initial information on a pregnancy must be reported to the Sponsor, and information on the outcome provided once it is available. Completed Pregnancy Surveillance Forms must be forwarded to the Sponsor according to SAE reporting procedures.

Note: Any pregnancy that occurs in a female partner of a male study subject must also be reported to the Sponsor using the Pregnancy Surveillance Form.

Protocol-required procedures for study discontinuation and follow up must be performed for the subject unless contraindicated. Other appropriate pregnancy follow up procedures should be considered if indicated. Information regarding the course of the pregnancy, including perinatal and neonatal outcome, must be reported to the Sponsor on the Pregnancy Surveillance Form. Infants should be followed for a minimum of 8 weeks.

7.12 OTHER SAFETY CONSIDERATIONS

Any significant worsening noted in electrocardiograms, x-rays, and any other potential safety or physical assessments, whether or not these procedures are required by the protocol, should also be recorded in the medical record.

8 STATISTICAL CONSIDERATIONS

8.1 PRIMARY AND SECONDARY ENDPOINTS

8.1.1 Primary Endpoint

The primary endpoint of the study is the change from baseline of VO₂MAX at the end of Period 2 of the study.

8.1.2 Secondary Endpoints

The secondary endpoints of the study are:

- The change from baseline of VO₂MAX at the end of study-drug dosing Period 1 compared to the change from baseline at the end of study-drug dosing Period 2.
- An evaluation of the change in VO₂MAX at the end of study-drug dosing Period 1 compared to baseline will be performed.
- The change from baseline of the QTcF interval at the end of study-drug dosing Period 1 compared to the change from baseline at the end of study-drug dosing Period 2

- The change from baseline at the end of study-drug dosing Period 2 in the Six-Minute Walk Test (6MWT) and change from baseline at the end of study-drug dosing Period 1 compared to the change from baseline at the end of study-drug dosing Period 2
- Safety data (AEs, ECG abnormalities, routine laboratory safety test of blood, vital signs, and concomitant medication and patient withdrawals) during study-drug dosing Period 1 compared to study-drug dosing Period 2

8.1.3 Exploratory Endpoints

Exploratory endpoints are:

- Change from baseline of other ECG variables at the end of study-drug dosing Period 1 compared to the change from baseline at the end of study-drug dosing Period 2
- Change from baseline of HbA1c at the end of study-drug dosing Period 1 compared to the change from baseline at the end of study-drug dosing Period 2

8.2 SAMPLE SIZE DETERMINATION

A two-sided, one-sample t-test of the change from baseline for the end of Period 2 is planned with the following assumptions:

- Mean change from baseline for Period 1 is 1.2mL O₂/kg/min
- Mean change from baseline for Period 2 is 2.0mL O₂/kg/min
- Standard deviation of change from baseline is 2.5mL O₂/kg/min for both periods
- Significance level (*alpha*) of 0.05

With these assumptions, a power of > 95% is anticipated for the primary outcome, and 72% for the first secondary outcome is expected for a sample size of 30 patients.

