
	
 e. History of cardiac transplantation f. Cardiac surgery or septal reduction surgery planned in the next 6 months or having occurred within the past 6 months g. HCM believed to be caused by infiltrative disorders, glycogen storage disorders, and/or hypertensive heart disease (including genotypic or phenotypic evidence of Fabry's Disease)
Study Procedures	
Dosing will be initiated at the Baseline Visit after successful completion of the Protocol Activities during this visit. Study medication will be taken once daily in the evening (preferably 8-11p.m., with the exception of the first dose of study drug, which will be administered under the supervision of the study-site staff) on an outpatient basis for 112 consecutive days. Patients should take the study medication with a glass of water or other non-alcoholic beverage, regardless of food intake.
 
All patients will be started at an initial dose of 70 mg (2 tablets) per day. After two weeks, dose level adjustment will be made every second week according to plasma level measurements for Period 1 according to the Dose Adjustment Guidelines and Algorithm (Table 1.1).
 
At the end of Period 1 (end of Week 8), all patients will undergo CPEX examination. Following the successful completion of Period 1, patients will undergo dose adjustment every second week according to the higher target therapeutic range for plasma levels defined for Period 2 (Table 1.1).
 
At the end of Period 2 (end of Week 16), all patients will undergo CPEX testing.

Statistical Analysis	
A two-sided, one-sample t-test of the change from baseline for the end of Period 2 is planned for VO₂MAX; a power of at least 72% is expected for a sample size of 30 patients for at least a mean change from baseline of 1.2mL O₂/kg/min.

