2.8 STUDY RATIONALE

This is an open-label, phase II study to confirm the optimal dosing regimen of PEX for use in a future phase III study in patients with HCM. The previous study [Abozguia, 2010] in HCM patients demonstrated that a safe and effective plasma concentration for PEX was 150-600 ng/mL. However, a more refined dosing study to evaluate safety and efficacy at low (100-300 ng/mL) and high (300-500 ng/mL) plasma PEX levels has not yet been performed. Potentially, equal efficacy with improved safety could be achieved at lower concentrations of PEX.

A population pharmacokinetic (PK) evaluation of the PK data from the PEX-TQT study was done to identify and characterize patient factors influencing PEX PK and the magnitude of unexplained PK variability [Mould, 2016]. Application of this newly developed model compared to a previously published model [Hussein *et al.*, 2001] showed the new model better describes PEX PK, particularly in extensive metabolizer (EM) and intermediate metabolizer (IM) groups.

The 2-compartment PK model developed from this exercise was used to predict drug exposures after single and multiple doses of PEX 70, 140, and 280 mg in all CYP2D6 genotypes [Mould, 2016]. Simulations of multiple dose administrations demonstrated that therapeutic levels of PEX in the range of 150-600 ng/mL for all the CYP2D6 genotypes eligible could be achieved in this study with doses of 70 to 280 mg daily. Figure 2.1 shows the initial response to 70 mg daily in IM, EM, and PM subjects, and clearly shows that all subjects, including phenotypic PM subjects can be safely dosed through two weeks without reaching

excessive PEX levels. However, conservatively, a blood sample to measure PEX and CIS levels will be obtained at day 8 to withdraw phenotypic PMs from the study. Then starting on day 15, PEX levels will continue to be measured every other week (Weeks 2, 4, 6, 8, 10, 12 and 14) in order to guide dose adjustment and to achieve the desired plasma concentrations. The following doses are expected to produce therapeutic concentrations in the majority of patients (PMs are being excluded from the study):

- Intermediate Metabolizers (IM): 70 to 140 mg daily
- Extensive Metabolizers (EM): 140 to 210 mg daily
- Ultra-rapid Metabolizers (UM): May require maximum doses of 210 (Period 1) or 280 (Period 2) mg daily. These subjects may not reach the target therapeutic level.

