7.2 Secondary Efficacy Analyses

7.2.1 *Difference between Period 2 and Period 1 Change from Baseline in VO₂MAX*

The first secondary efficacy endpoint is the change from Baseline of VO₂MAX at the end of Period 1 compared to the change from Baseline at the end of Period 2. This will be analyzed using an ANCOVA with covariates of baseline VO₂MAX and the Period-mean plasma PEX level for the Completer Population. The estimated mean change in VO₂MAX from Baseline to Period 1 and to Period 2 and the difference between Period 1 and Period 2 will be presented along with a 95% confidence interval and the p-value. This analysis will be repeated for the MITT, and will include any imputed change in VO₂MAX as in the primary analysis.

Example SAS code is shown below:

```
proc mixed data=dataP1P2;  
  class Period;  
  model CHG=BASE PEXP1P2 Period/ solution cl;  
  lsmeans Period/ cl diffs;  
  estimate "Period 2 vs. Period 1" Period -1 1/ cl;  
run;
```

7.2.2 *Change from Baseline in VO₂MAX at the end of Period 1*

The second secondary efficacy endpoint is the change from Baseline of VO₂MAX at the end of Period 1. Similar to the primary efficacy endpoint, this will be analyzed using an ANCOVA with covariates of baseline VO₂MAX and the Period 1 mean plasma PEX level for the Completer Population. This will be repeated for the MITT, including any imputed change in VO₂MAX values for patients who did not complete the study to the end of Period 1. Descriptive statistics of the Baseline value, VO₂MAX at the end of Period 1 and the change from Baseline to end of Period 1 will be presented for the Completer Population and the MITT Population.

7.2.3 *Change from Baseline in 6MWT at the end of Period 2*

The change from Baseline in the 6MWT at the end of Period 2 will be analyzed using an ANCOVA with covariates of baseline VO₂MAX and the Period 2 mean plasma PEX level. This will be presented for the Completer Population and repeated for the MITT including any imputed change from Baseline values for patients who did not complete the study to the end of Period 2.

7.2.4 *Difference between Period 2 and Period 1 Change from Baseline in 6MWT*

The change from Baseline in the 6MWT at the end of Period 1 compared to the change from Baseline at the end of Period 2 will be analyzed using an ANCOVA with covariates of baseline VO₂MAX and the Period-mean plasma PEX level Completer Population and repeated for the MITT.

7.2.5 *Change from Baseline in 6MWT at the end of Period 1*

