11 SAMPLE SIZE AND POWER CONSIDERATIONS

The sample size was based on a two-sided, one-sample t-test of the change from Baseline for the end of Period 2 with the following assumptions:

- Mean change from Baseline for Period 1 is 1.2mL O₂/kg/min
- Mean change from Baseline for Period 2 is 2.0mL O₂/kg/min
- Standard deviation of change from Baseline is 2.5mL O₂/kg/min for both periods
- Significance level (alpha) of 0.05

With these assumptions, a power of > 95% is anticipated for the primary outcome, and 72% for the first secondary outcome is expected for a sample size of 30 patients.

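### The 72% power stated for the first secondary outcome belongs to the second; the Period 2 versus Period 1 comparison has about 22% to 59% power for within-patient correlations from 0 to 0.7

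*Protocol*

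**What the plan says.** Protocol 8.2 introduces its assumptions with "A two-sided, one-sample t-test of the change from baseline for the end of Period 2 is planned with the following assumptions". They are a mean change of 1.2 mL O₂/kg/min in Period 1 and 2.0 in Period 2, an SD of change of 2.5 in each period, and alpha 0.05. It concludes: "With these assumptions, a power of > 95% is anticipated for the primary outcome, and 72% for the first secondary outcome is expected", for 30 patients. SAP 11 keeps the same assumptions and the same claim: "72% for the first secondary outcome is expected for a sample size of 30 patients".

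The SAP settles which outcome is meant. Section 7.2.1, on the difference between the Period 2 and Period 1 changes in VO₂MAX, opens "The first secondary efficacy endpoint is the change from Baseline of". Section 7.2.2, on the Period 1 change from baseline, opens "The second secondary efficacy endpoint is the change from Baseline of". Protocol 8.1.2 lists the two in the same order.

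The Statistical Analysis row of the Protocol synopsis uses the 72% differently: "a power of at least 72% is expected for a sample size of 30 patients for at least a mean change from baseline of" 1.2 mL O₂/kg/min. That is the mean assumed for the Period 1 change from baseline.

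**The concern.** The figure of 1.2 enters the assumptions as the Period 1 change from baseline ("Mean change from baseline for Period 1 is 1.2mL"). The endpoint named in the power sentence is a contrast between two changes in the same patients, for which the assumptions imply a mean of 0.8. The power of that contrast also needs the SD of the within-patient difference or, equivalently, the correlation between the two changes. Neither document gives either, so 72% cannot be derived for the named endpoint from the listed inputs.

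The contrast matters. It is the formal VO₂MAX comparison of the two plasma ranges and serves the dose-response objective. The study is meant to confirm a regimen for phase 3, and Protocol 2.8 raises the possibility directly: "Potentially, equal efficacy with improved safety could be achieved at lower concentrations of PEX". A reader who believes the comparison had 72% power may take a non-significant result as support for that idea, although a true 0.8 advantage for the higher range could easily have been missed.

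**Working it through.** **Inputs** (Protocol 8.2 and SAP 11): means 1.2 and 2.0, SD 2.5 in each period, n = 30, two-sided alpha 0.05. The correlation ρ between a patient's Period 1 and Period 2 changes is not stated, so it is varied as an assumption.

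**Method.** For a one-sample or paired t-test with mean δ and SD s, the noncentrality is δ√n / s with n − 1 = 29 degrees of freedom. Power is the probability that a noncentral t variable falls beyond ±2.045.

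**Step 1: reproduce the stated figures.**

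- Primary, Period 2 change from baseline: 2.0 × √30 / 2.5 = 4.38, power 98.8%. This agrees with the stated >95%.
- Period 1 change from baseline: 1.2 × √30 / 2.5 = 2.63, power 71.9%. This is the stated 72%.

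So the 72% is correct arithmetic for the Period 1 change from baseline, which is also how the synopsis uses it.

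**Step 2: power for the named first secondary endpoint.** The mean difference is 2.0 − 1.2 = 0.8. With equal SDs, the SD of the difference is 2.5 × √(2(1 − ρ)).

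| Assumed ρ | SD of difference | Noncentrality | Paired t-test power |
|---|---|---|---|
| 0 | 3.54 | 1.24 | 22.4% |
| 0.3 | 2.96 | 1.48 | 29.9% |
| 0.5 | 2.50 | 1.75 | 39.6% |
| 0.6 | 2.24 | 1.96 | 47.4% |
| 0.7 | 1.94 | 2.26 | 59.0% |
| 0.8 | 1.58 | 2.77 | 76.4% |
| 0.85 | 1.37 | 3.20 | 87.1% |

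Power passes 50% at ρ of about 0.63. It reaches 72% at ρ of about 0.78, where the SD of the difference is 1.67.

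**Step 3: sensitivity over ρ from 0 to 0.7.** A normal approximation gives 23.6% to 61.9%. All 33 enrolled patients instead of 30 gives 24.3% to 63.4%. No two-sided variant reaches 72% in this range.

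**Step 4: patients needed.** For 72% power to detect 0.8 with a paired t-test, 66 patients would be needed at ρ = 0.5 and 40 at ρ = 0.7, against 30 expected completers.

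**The case against.** The strongest reply is that this is a labelling slip already half disclosed. The 72% is computed correctly, the synopsis ties it to a change of 1.2, and the same synopsis runs the two VO₂MAX secondary endpoints together under one bullet. That explains how the slip arose, but the SAP's ordinal labels leave no doubt about which endpoint is first, and SAP 11 repeats the sentence unchanged.

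Second, ρ may be high. The two changes share one baseline, which pushes ρ upward: with equal variances and equal correlations across the three visits, ρ is exactly 0.5. The 22% at ρ = 0 is therefore a pessimistic end, and from about 0.78 upward the comparison would have 72% or more. This stands as a limit on the claim. Saying that a true 0.8 difference would more likely than not be missed holds only for ρ below about 0.63. It does not rescue the stated figure, because no such correlation is stated and the synopsis shows where the 72% came from.

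Third, the SAP no longer plans a t-test. Sections 7.2.1 and 12 move to ANCOVA with baseline VO₂MAX and mean plasma PEX as covariates, and its power cannot be computed from the documents. That is a fair caution: any restated power must name its test. SAP 11 itself still describes the sizing as based on a t-test. Nor does the change clearly help. The example code in 7.2.1 has no REPEATED or RANDOM statement, so as written it treats a patient's two changes as independent. A simulation of such an analysis without covariates gives power of about 23% at ρ = 0, 15% at 0.5 and 7% at 0.8. The code is only an example, so this is supporting evidence.

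Finally, neither document says that non-significance will be read as equal efficacy, and SAP 7.2.1 already plans a 95% confidence interval. Both points are true. The risk of misreading is an inference from the study rationale, and part of the safeguard already exists.

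**Conclusion.** The concern holds. The stated 72% is wrong for the endpoint it names and right for the one the SAP ranks second. For the Period 2 versus Period 1 comparison, the documents' own means and SD give paired t-test power between 22% (ρ = 0) and 59% (ρ = 0.7), with 40% at ρ = 0.5; 72% requires ρ of about 0.78.

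These figures assume 30 completers, a true difference of 0.8, equal SDs of 2.5 and two-sided alpha 0.05. The correlation is an assumption throughout, and the power of the planned ANCOVA is unknown. The primary endpoint's power is unaffected and reproduces.

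**What to change.** In Protocol 8.2 and SAP 11:

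1. Attach the 72% to the Period 1 change from baseline in VO₂MAX, identified as the second secondary endpoint.
2. For the Period 2 versus Period 1 comparison, state the assumed within-patient correlation (or SD of the difference), the test, and the resulting power. For example: paired t-test, difference 0.8, n = 30, about 40% at a correlation of 0.5, ranging from 22% to 76% for correlations of 0 to 0.8. Label this as paired t-test power, since the planned analysis is now an ANCOVA.
3. Add that a non-significant difference between periods will not be interpreted as equal efficacy, and that the conclusion rests on the 95% confidence interval already planned in SAP 7.2.1.

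The cost is wording in two sections and a less favourable stated power. No patients, visits or procedures are added, and the sample size does not change.
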